6.2.4 Multiplicity Adjustment

No multiplicity adjustments will be made in this study. Two-sided 90% confidence interval (CI) will be used to describe the precision of the rate estimate whenever appropriate.

6.2.5 Patient Disposition

The following patient disposition information will be summarized:

- Number of patients treated
- Number (%) of treated patients who discontinued from treatment
- Reason(s) for treatment discontinuation
- Number (%) of treated patients who discontinued from study
- Reason(s) for study discontinuation
- Number (%) of treated patients who remain in study
- Study follow-up time: defined as the time from the first dose date to death date or end of study date (whichever occurred first) for patients who discontinued study or the data cutoff date for ongoing patient

6.2.6 Protocol Deviations

Major protocol deviation criteria will be established and patients with major protocol deviations will be identified and documented before the database lock. Major protocol deviations will be summarized for the SAF. Also a listing of Covid-19 related protocol deviations will be summarized if applicable.

6.2.7 Demographics and Other Baseline Characteristics

Demographics and baseline characteristics including following variables will be summarized using descriptive statistics:

- Age (years) and age group (years) as < 65 , ≥ 65
- Gender
- Race
- Baseline Eastern Cooperative Oncology Group (ECOG) performance status
- Ethnicity
- Tobacco use
- Height
- Weight

6.2.8 Disease History

The number (percentage) of subjects reporting a history of disease and characteristic, as recorded on the eCRF, will be summarized in the SAF. Disease characteristics include time from initial diagnosis to study entry, type of solid tumor (if applicable), locations of metastases, MSI-H mutation, hormone status, tumor histology/cytology, Germline BRCA mutation, somatic BRCA mutation and HRD status.

A subject data listing of disease history will be provided.

6.2.9 Prior Anti-Cancer Systemic Therapies

The number of patients with prior anticancer surgeries, prior systemic therapies, prior radiation therapies will be summarized by cohort and all patients for the SAF. The therapies and surgeries with the same sequence/regimen number are counted as one prior therapy/surgery.

A subject data listing of prior anticancer drug therapies, prior anticancer surgeries and prior radiation therapies will be provided.

6.2.10 Prior and Concomitant Medications

Prior and concomitant medications will be coded using the version of World Health Organization Drug Dictionary (WHO DD) drug codes currently in effect at BeiGene at the time of database lock and will be further classified to the appropriate Anatomical Therapeutic Chemical (ATC) code.

The number and percentage of patients reporting prior and concomitant medications will be summarized by ATC medication class and WHO DD preferred term for the Safety Analysis Set by cohort and overall. Prior medications are defined as medications that started and ended before the first dose date. Concomitant medications will be defined as medications that (1) started before the first dose of study treatment and were continuing at the time of the first dose of study treatment, or (2) started on or after the date of the first dose of study treatment up to 30 days after the patient's last dose of pamiparib or initiation of a new anticancer therapy. A listing of prior and concomitant medications will be provided.

6.2.11 Medical History

Medical History will be coded using MedDRA (version 23.0). The number and percentage of patients reporting a history of any medical condition, as recorded on the CRF, will be summarized by system organ class (SOC) and preferred term (PT) for the Safety Analysis Set by cohort and overall. A listing of medical history will be provided.

6.3 EFFICACY ANALYSIS

6.3.1 Primary Efficacy Endpoints

Escalation:

- Dose-limiting toxicity in the DLT evaluation period will be used to determine the dose and schedule of pamiparib plus TMZ in the expansion cohorts. The DLT events will be listed for patients in the DLT Evaluable Analysis Set.

All phases:

- Incidence, nature, and severity of AEs will be summarized. Refer to Section 6.4.3 for more detail. The outputs for AEs will be summarized in SAF.
- Overall Response Rate (ORR) by investigator

Tumor status evaluation including response and progression will be assessed using RECIST v1.1 by investigator throughout this study. This criterion will be used to calculate tumor assessment endpoints including ORR, DCR, DOR and PFS.

ORR is defined as the proportion of subjects who have a best overall response (BOR) of complete response (CR) or partial response (PR), where BOR is defined as the best response recorded from the first postbaseline tumor assessment until data cutoff date, disease progression or start of new anticancer treatment. For a confirmed ORR, confirmation of CR or PR at next tumor scan (at least 4 weeks from initial documentation) is required.

Two-sided binomial exact 90% confidence intervals (CI) of ORR will also be constructed for the statistical inference of the point estimate in each cohort.

Tables for confirmed and nonconfirmed ORR will be summarized in Efficacy Evaluable Analysis Set. In addition, a listing of the tumor assessment data in SAF will also be provided. Patients without evaluable postbaseline tumor assessment will be considered as non-responders in the safety analysis set. Maximum tumor shrinkage per patient will be presented in waterfall plots.

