Anti-tumor activity will be evaluated by the treating investigator using standard RECIST v1.1 criteria (Appendix 5). Tumor response will also be evaluated according to the Gynecologic Cancer Intergroup (GCIg) criteria for patients with ovarian cancer. In addition, the Prostate Cancer Clinical Trials Working Group 2 (PCWG2) criteria will be used for patients with prostate cancer.

Patients who, at the time of progression, have an ongoing AE that leads to treatment discontinuation, will be followed until the event resolves, the investigator assesses the event as stable, the patient is lost to follow-up, or the patient starts a different anti-tumor therapy. If a patient discontinues study drug due to reasons other than disease progression or death, then tumor assessments should continue to be performed following the scheduled assessment plan until the start of new anticancer therapy, disease progression, death, lost to follow-up, or withdrawal of consent to efficacy follow-up.

In the absence of unacceptable toxicities or disease progression, patients will be offered continued study treatment of BGB-290 plus TMZ. Regardless of discontinuation of one or more study drugs, patients should continue on study with regular follow-up (Section 8.5). Patients who have discontinued all study drugs should return to the clinic for an end-of-treatment (EOT) visit within 7 days after the last study treatment (Section 8.4). After the EOT visit, patients should have regular follow-up for safety, efficacy, and survival as outlined in Section 8.5.

Study procedures and assessments are further detailed in Section 7 and Section 8, and a Schedule of Assessments can be found in [Appendix 1 Table 1](#).

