11.2.5. Efficacy Analyses

No formal hypothesis testing is planned in this Phase 1b study.

For solid tumors other than prostate cancer, tumor assessment based on investigator assessment according to RECIST v1.1 will be used to calculate ORR, DCR, PFS, and DOR, as well as timepoint estimate PFS-6m. Overall survival (OS) and OS-6m will be summarized as well. For patients with ovarian cancer, tumor response may also be assessed by investigators based on GCIG criteria which use carcinoma antigen-125 (CA-125) in combination with RECIST v1.1 ([Appendix 9](#)).

For patients with prostate cancer, PSA and tumor lesions will be evaluated together to determine the tumor response according to PCWG2 criteria ([Appendix 10](#)).

ORR is defined as the proportion of patients who have a best overall response (BOR) of CR or PR, where BOR is defined as the best response recorded from the first dose of study drugs until data cut, disease progression, or start of new anti-neoplastic treatment. Binomial exact 90% and 95% confidence intervals will be calculated for ORR in each cohort.

DCR is defined as the proportion of patients with BOR of CR, PR, and SD. It will be summarized similarly as ORR.

PFS is defined as the time from the date of the first dose of study drugs to disease progression or death, whichever occurs first.

PFS censoring rule will follow FDA *Guidance for Industry, Clinical Trial Endpoints for Approval of Cancer drugs and Biologics* (2007). Patients who have a clinical determination of progression should undergo imaging and laboratory assessments, if possible, to correlate radiographic findings with the clinical findings. Data for patients without disease progression or death by the time of analysis will be censored at the time of the last tumor assessment. Data from patients who are lost to follow-up prior to documented disease progression will be censored at the last tumor assessment date when the patient is known to be progression-free. More details will be given in the SAP.

DOR is defined as the time from the date of the earliest documented response to disease progression or death for any cause, whichever occurs earlier. Only responders will be included in the DOR calculation.

OS is defined as the time from the date of the first dose of study drugs to death.

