
Bone
	
≥ 2 new lesions at the first scheduled reassessment ≤ 13 weeks from Cycle 1 Day 1 compared with baseline must be confirmed by a second scan performed 6 or more weeks later.
 
Confirmatory scans should show an additional 2 new lesions compared to the first post-treatment scan (i.e. a total of ≥ 4 new lesions compared with the baseline bone scan).
 
Confirm ambiguous results by other imaging modalities (e.g., CT or MRI).
 
Investigators are highly encouraged to maintain the patient's treatment with study medication unless progression is confirmed.
 <hr/> 
≥ 2 new lesions at the first scheduled reassessment > 13 weeks from Cycle 1 Day 1 compared with baseline must be confirmed by a second scan performed 6 or more weeks later.
 
Confirmatory scans should confirm the presence of the 2 new lesions compared to the baseline scan. (i.e. a total of ≥ 2 new lesions compared with the baseline bone scan).
 
Confirm ambiguous results by other imaging modalities (e.g., CT or MRI).
 
Investigators are highly encouraged to maintain the patient's treatment with study medication unless progression is confirmed.

CT: computed tomography; MRI: magnetic resonance imaging; PCWG2: Prostate Cancer Clinical Trials Working Group 2;
 PET: positron emission tomography; PSA: prostate-specific antigen; PSA-DT: PSA doubling-time;
 RECIST: Response Evaluation Criteria in Solid Tumors

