10.2 CENSORING RULES

Table 3 shows the primary censoring rules for the derivation of PFS.

Table 3 Censoring Rules for Analysis of PFS

No.	Situation	Date of Progression or Censoring	Outcome
1	No baseline tumor assessments or no post baseline tumor assessment	Reference start date (e.g., C1D1)	Censored
2	Progression documented on scheduled visit or between scheduled visits	Date of first radiologic PD assessment	Progressed
3	No progression at the time of data cutoff or withdrawal from study	Date of last adequate radiologic assessment prior to or on date of data cutoff or withdrawal from study	Censored
4	Treatment discontinuation for undocumented progression	Date of last radiological assessment of measured lesions	Censored
5	New anticancer treatment started	Date of last radiological assessment of measured lesions prior to or on date of new anticancer treatment	Censored
6	Death before first PD assessment	Date of death	Progressed
7	Death between adequate assessment visits*	Date of death	Progressed
8	Death or PD after two or more consecutive missed visit**	Date of last adequate radiologic assessment before missed tumor assessments	Censored

9	A patient meets the criteria for more than 1 censoring rules above	Date of the earliest censoring date among all events	Censored
---	--	--	----------

Abbreviations: CR=complete response, PD=progressive disease, PR=partial response, SD=stable disease.

*Adequate tumor assessment is a radiologic assessment of CR, PR, SD, non-CR/non-PD or PD as determined by investigators or by IRC.

**More than one missed visit is defined if the duration between the last tumor assessment and death or PD is longer than 2 scheduled visits, which is 17 weeks (119 days).

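### For prostate cancer the SAP uses RECIST progression without the protocol's PCWG2 bone-scan confirmation, and does not declare the change

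*SAP*

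**What the plan says.** **SAP.** Section 6.3.1 says: "Tumor status evaluation including response and progression will be assessed using RECIST v1.1 by investigator throughout this study". It continues: "This criterion will be used to calculate tumor assessment endpoints including ORR, DCR, DOR and PFS". Neither sentence makes an exception for Cohort 3. Row 2 of Table 3 (Section 10.2) gives the PFS event date as "Date of first radiologic PD assessment", and no row asks for confirmation. Under 6.3.1, best overall response is collected only until progression, data cutoff or new anticancer therapy. PSA is confined to a listing (6.3.5). In the SAP text available, PCWG2 does not appear; PCWG3 and radiographic PFS appear only among the abbreviations. Section 8 says that ORR, PFS and DOR will rest on radiographic findings. It does not mention PCWG2 or bone-scan confirmation.

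**Protocol.** Section 11.2.5 separates the diseases. "For solid tumors other than prostate cancer, tumor assessment based on investigator assessment according to RECIST v1.1 will be used to calculate ORR", and the sentence goes on to DCR, PFS and DOR. Then: "For patients with prostate cancer, PSA and tumor lesions will be evaluated together to determine the tumor response according to PCWG2 criteria". Section 4.1 names RECIST v1.1 as the standard and adds: "In addition, the Prostate Cancer Clinical Trials Working Group 2 (PCWG2) criteria will be used for patients with prostate cancer". In the bone row of Appendix 10, a finding of two or more new lesions "must be confirmed by a second scan performed 6 or more weeks later". If it is first seen by 13 weeks, the confirmatory scan must show two further new lesions. If it is first seen later, the original two must still be present. The same row encourages keeping the patient on study medication unless progression is confirmed.

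Protocol 3.1, however, lists ORR by RECIST v1.1 as a primary endpoint with no prostate exception.

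**The concern.** The two documents use different definitions of progression for the same patients. RECIST, as reproduced in Protocol Appendix 5, treats one or more new lesions as progression. Appendix 10 does not accept early new bone lesions in prostate cancer as progression until a later scan shows more of them.

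A patient followed under Appendix 10 could therefore remain on treatment, later show a soft-tissue response, and still be analysed as having progressed at the first scan. PFS would end there. A response after that date could not count toward ORR, because the best-response window closes at progression. DCR would lose a patient who was otherwise stable, and an existing response could have its duration cut short.

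The radiographic basis declared in SAP Section 8 explains why PSA was dropped. It does not explain dropping the bone confirmation, which is itself a radiographic rule.

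**Working it through.** **1. The rules side by side, for prostate cancer**

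| Item | Protocol 11.2.5 and Appendix 10 | SAP 6.3.1 and Table 3 |
|---|---|---|
| Criterion | PCWG2, PSA with lesions | RECIST v1.1, investigator |
| New bone lesions | Two or more, confirmed at least 6 weeks later | Progression if the investigator records PD |
| First seen by 13 weeks | Two additional new lesions on confirmation | No separate rule |
| Confirmation of PD | Required for bone | None |

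**2. Timing.** Protocol 7.7 sets imaging every 8 weeks ± 7 days from Cycle 1 Day 1, so an on-schedule first assessment falls in weeks 7 to 9, inside the 13-week period. With the SAP's month of 30.4375 days:
- week 8: 56 / 30.4375 = 1.84 months (weeks 7 to 9: 1.61 to 2.07);
- week 16: 112 / 30.4375 = 3.68 months.

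Consecutive on-schedule scans at weeks 7 to 9 and 15 to 17 lie 6 to 10 weeks apart. That meets the 6-week interval when bone imaging was done at both.

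**3. Who is affected.** The SAP efficacy-evaluable set (6.1) requires measurable disease in expansion and omits the protocol's allowance for prostate patients entering under inclusion criterion 14f. Bone-only Cohort 3 patients are therefore outside the ORR and PFS tables. The exposed group is those with both measurable and bone disease.

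**4. The plan's own ORR figures.** The exact (Clopper-Pearson) 90% interval for x responders in n patients is
- lower limit = 0.05 quantile of Beta(x, n − x + 1);
- upper limit = 0.95 quantile of Beta(x + 1, n − x).

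All ten rows of SAP Table 1 reproduce to the rounded percent. For example, 8/20 gives 21.7% to 60.6% (stated 22% to 61%) and 10/25 gives 23.6% to 58.3% (stated 24% to 58%).

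**5. Effect of each lost responder.** One patient is 1/25 = 4 points or 1/20 = 5 points.

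| Responders lost | n = 20 | n = 25 |
|---|---|---|
| 0 | 8/20 = 40% (21.7% to 60.6%) | 10/25 = 40% (23.6% to 58.3%) |
| 1 | 7/20 = 35% (17.7% to 55.8%) | 9/25 = 36% (20.2% to 54.4%) |
| 2 | 6/20 = 30% (14.0% to 50.8%) | 8/25 = 32% (17.0% to 50.4%) |

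SAP Section 5 argues that the design is adequate because the lower limit is above 20%. At n = 20 one lost responder takes it below; at n = 25 it takes two.

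**6. Range under an assumption.** The documents give no rate of unconfirmed early bone findings. Suppose a fraction f of patients who would otherwise respond are recorded as PD for this reason. Expected ORR is 40% × (1 − f), and the chance of losing at least one of 8 responders is 1 − (1 − f)^8. For f = 5%, 10% and 20%, expected ORR is 38%, 36% and 32%, and the chance is 34%, 57% and 83%. These values of f are illustrative only.

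**The case against.** **Appendix 5 already guards against flare.** It requires a new lesion to be unequivocal, cites healing or flare of existing bone lesions as a false signal, and allows an equivocal lesion to be followed before progression is declared. An investigator who suspects flare need not record PD. This stands as a limit: a reader might infer that any flare ends PFS, but it does so only when the investigator records it as PD. It does not remove the conflict, because Appendix 5 leaves the matter to judgement and has no rule for two additional lesions.

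**The protocol is not uniform.** Section 3.1 names RECIST for ORR without exception, and 4.1 adds PCWG2 to RECIST. It would be too strong to say that the SAP simply departs from a clear protocol rule for ORR. For PFS, DOR and DCR there is no such competing text, and 11.2.5 governs.

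**Exposure is narrower than the calendar suggests.** Because every on-schedule first scan precedes week 13, a reader might infer that the whole cohort is at risk, or apply an assumed flare rate to all 20 to 25 patients. The measurable-disease requirement, the lack of any flare rate, and the need for a later soft-tissue response before ORR is affected rule that out.

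**Bone imaging may be incomplete.** Protocol 7.7 includes bone scans for patients with bone metastasis but then makes later ones depend on clinical indication, and Appendix 1 has no bone-scan row. It cannot be assumed that every early finding has a scan to confirm it.

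**No test depends on this.** The study is descriptive, and tumor assessments and PSA are listed by patient. That lowers the stakes, but the reported Cohort 3 estimates would still rest on a definition that 11.2.5 does not give.

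**Conclusion.** The conflict holds. The SAP replaces the protocol's PCWG2 derivation for prostate cancer with RECIST and unconfirmed progression, and Section 8 does not say so. Dating progression at the first scan is not in itself the fault; the missing bone confirmation is.

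The consequence is possible rather than certain. In Cohort 3 patients with measurable and bone disease, new bone lesions recorded as PD at week 8 could set PFS at about 1.8 months and close the best-response window while Appendix 10 would still await confirmation. The size of the bias cannot be computed from the documents. What can be stated is the effect per patient, 4 to 5 ORR points, and that one lost responder among 20 takes the exact 90% lower limit from 21.7% to 17.7%. That assumes the planned cohort size and an ORR near 40%.

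The point should be settled before the Cohort 3 analysis, since that cohort is reported in both the interim and the final study report.

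**What to change.** In SAP 6.3.1, 6.3.2 and Table 3, derive progression for prostate-cancer patients with the Appendix 10 bone-confirmation rule, and carry it through PFS, DOR, DCR and best overall response. Three details need stating:
- **Dating of confirmed bone progression.** The bone row of Appendix 10 gives no dating rule. Appendix 5 dates a later-confirmed equivocal lesion to its first scan, which is a precedent.
- **New bone lesions without a confirmatory bone scan.** Say whether such a patient has an event, is censored, or continues in follow-up.
- **Data source.** Use bone imaging already collected.

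Report the RECIST-only result as a sensitivity analysis.

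If RECIST is to stay primary for ORR because of Protocol 3.1, declare the departure from Protocol 11.2.5 in SAP Section 8 and give the PCWG2-based result as the sensitivity analysis. Either way, Protocol 3.1, 4.1 and 11.2.5 and SAP 6.3.1 should be reconciled.

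The cost is SAP wording and one extra programming rule for one tumor type. The derivation becomes slightly more complex, and some early bone findings may stay unconfirmed where no follow-up bone scan was done.

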6.1 ANALYSIS POPULATIONS

- Safety Analysis Set (SAF): includes all patients enrolled into the study who receive any dose of pamiparib and/or TMZ. The Safety Analysis Set will be used for overall survival analysis and safety analyses.
- Efficacy-Evaluable Analysis Set: includes patients in the SAF who had evaluable disease in the dose escalation phase (or measurable disease in the dose expansion phase) at baseline and had at least one postbaseline tumor assessment unless discontinued treatment due to clinical progression or death prior to tumor assessment.

Evaluable disease means patients may have measurable (target lesions) or non-measurable lesions (non-target lesions); measurable disease means patients must have at least 1 measurable lesion (target lesions) and may or may not have non measurable lesions (non-target lesions).

- DLT Evaluable Analysis Set: includes patients who received $\geq 70\%$ of BGB-290 and TMZ during the DLT assessment window (Cycle 1). Additionally, patients who had a DLT event during the DLT assessment window despite receiving $< 70\%$ of the scheduled dose will also be included.
- PK Analysis Set: includes patients who received any dose of BGB-290 or TMZ, and contributed at least one plasma concentration.

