6.3.2 Secondary Efficacy Endpoints

- Pharmacokinetic parameters of BGB-290 and TMZ, including but not limited to C_{trough}
Refer to Section 6.3.6 for more detail.
- Disease Control Rate (DCR) by investigator

DCR is defined as the proportion of subjects with BOR of CR, PR, or stable disease (SD). Similar to ORR, two-sided binomial exact 90% confidence intervals will be calculated for DCR in each cohort. The table for DCR will be summarized in both SAF and Efficacy Evaluable Analysis Set. Patients without evaluable postbaseline tumor assessment will be considered as non-responders in the safety analysis set.

- Duration of Response (DOR) by investigator

DOR is defined as the time (month) from the date of the earliest documented CR or PR (that is subsequently confirmed) to disease progression or death due to any cause, whichever occurs earlier. The tables for confirmed and nonconfirmed DOR will be summarized in efficacy evaluable set and only responders will be included in the DOR calculation.

Kaplan-Meier method will be used to estimate DOR, and corresponding quartiles (including the median) in the responders. A two-sided 90% CIs of median will be calculated for each cohorts using generalized Brookmeyer and Crowley method (Brookmeyer & Crowley, 1982).

Censoring rule for DOR will follow PFS censoring rule mentioned in FDA Guidance for Industry Clinical Trial Endpoints for the Approval of Cancer Drugs and Biologics (2018). The censoring rules are described in Appendix 10.2.

- PFS and PFS-6m by investigator

PFS is defined as the time (months) from the date of the first dose of combination treatment to disease progression or death due to any cause, whichever occurs first. The PFS-6m is defined as the percentages of subjects who remain alive and progression-free at 6 months. PFS censoring rules are described in Appendix 10.2. If a patient meets the criteria for more than 1 censoring rule, PFS will be censored at the earliest censoring date. The tables for PFS and PFS-6m will be summarized in Efficacy Evaluable Analysis Set.

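### The primary ORR is tabulated only in the Efficacy-Evaluable set; the SAP's all-treated non-responder rule feeds no ORR table, although DCR is tabulated in both sets

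*SAP*

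**What the plan says.** ORR by RECIST v1.1 is a primary endpoint (SAP 4.1). SAP 6.3.1 assigns its tables to one set: "Tables for confirmed and nonconfirmed ORR will be summarized in Efficacy Evaluable Analysis Set". For SAF it continues: "In addition, a listing of the tumor assessment data in SAF will also be provided". It then adds: "Patients without evaluable postbaseline tumor assessment will be considered as non-responders in the safety analysis set".

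SAP 6.3.2 repeats that rule for the secondary endpoint DCR and does give it a table: "The table for DCR will be summarized in both SAF and Efficacy Evaluable Analysis Set".

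SAP 6.1 limits the Efficacy-Evaluable set to SAF patients with suitable disease at baseline who "had at least one postbaseline tumor assessment unless discontinued treatment due to clinical progression or death prior to tumor assessment". Suitable disease differs by phase. In escalation: "Evaluable disease means patients may have measurable (target lesions) or non-measurable lesions (non-target lesions"). In expansion the requirement is "or measurable disease in the dose expansion phase) at baseline".

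SAP Section 8, which lists changes to the planned analysis, moves OS to SAF and adds no SAF table for ORR.

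**The concern.** A rule that counts patients as non-responders has an effect only where a rate is calculated. SAP 6.3.1 states such a rule for SAF but plans no SAF rate for ORR. The secondary endpoint therefore has an all-treated estimate with its exact interval, and the primary efficacy endpoint has none.

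The patients left out are treated patients with no postbaseline scan for reasons other than clinical progression or death: withdrawal, loss to follow-up, early new anticancer therapy, or an early stop without imaging. None of them can be a responder, so removing them shrinks the denominator and leaves the numerator unchanged. Any bias goes upward.

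Two smaller matters sit in the same place:

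- Neither ORR version, confirmed or nonconfirmed, is labeled primary.
- Protocol 11.2.1 keeps prostate patients who qualify under inclusion criterion 14f in the efficacy set. SAP 6.1 requires measurable disease in expansion and has no such exception. Read literally, Cohort 3 patients with only non-measurable bone lesions enter no ORR table.

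**Working it through.** **1. Which outputs are planned**

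| Endpoint | Efficacy-Evaluable set | SAF |
|---|---|---|
| ORR, primary (SAP 6.3.1) | Tables, confirmed and nonconfirmed | Listing of tumor data; non-responder rule stated |
| DCR, secondary (SAP 6.3.2) | Table | Table; same non-responder rule |

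No other section of either document names a SAF table for ORR. The subgroup summary for small cell lung cancer (SAP 6.3.3) does not state its set.

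**2. Reproducing the plan's own intervals**

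SAP 6.3.1 specifies exact binomial two-sided 90% intervals. For x responders among n patients, the lower limit is the 0.05 quantile of Beta(x, n − x + 1) and the upper limit is the 0.95 quantile of Beta(x + 1, n − x).

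- 8/20 = 40.0%: 21.7% to 60.6% (SAP Table 1: 22% to 61%).
- 10/25 = 40.0%: 23.6% to 58.3% (SAP Table 1: 24% to 58%).

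All ten rows of SAP Table 1 match after rounding, so the method is the one the plan uses.

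**3. Effect of the denominator**

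Let N be the number treated, k the number dropped as unscanned, and x the number of responders. The SAF rate is x/N, the Efficacy-Evaluable rate is x/(N − k), and the difference is x/(N − k) − x/N, which is zero at k = 0 and positive for k > 0 whenever x > 0.

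The documents give no value for k, so k = 0, 2 and 4 are assumptions, and 4 of 25 is an upper illustration. N = 25 is the top of the planned cohort size. The confirmed rows assume that one of the eight responses is not confirmed. Each comparison keeps the response definition fixed.

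| Version | Set | Rate | Exact 90% CI | Difference from SAF |
|---|---|---|---|---|
| Nonconfirmed | SAF, or k = 0 | 8/25 = 32.0% | 17.0% to 50.4% | 0 |
| Nonconfirmed | k = 2 | 8/23 = 34.8% | 18.6% to 54.0% | 2.8 points |
| Nonconfirmed | k = 4 | 8/21 = 38.1% | 20.6% to 58.3% | 6.1 points |
| Confirmed | SAF, or k = 0 | 7/25 = 28.0% | 13.9% to 46.2% | 0 |
| Confirmed | k = 2 | 7/23 = 30.4% | 15.2% to 49.6% | 2.4 points |
| Confirmed | k = 4 | 7/21 = 33.3% | 16.8% to 53.6% | 5.3 points |

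At the planning rate of about 40%, 8 responders among 20 treated give 40.0% in SAF and 8/18 = 44.4% with k = 2 (4.4 points). With 10 responders among 25 treated, the figures are 40.0% and 10/23 = 43.5% (3.5 points).

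**4. Against the plan's precision statement**

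SAP Section 5 argues that the lower limit exceeds 20% when the observed ORR is about 40%. An Efficacy-Evaluable result of 8/20 has a lower limit of 21.7%. If two further treated patients were never scanned, the SAF result is 8/22 = 36.4% with a lower limit of 19.6%.

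**The case against.** The strongest case on the other side is that this is a small drafting gap.

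- **No decision depends on it.** The study has no formal hypothesis test, and the 20% bound is a planning remark. This stands: the point concerns complete reporting and freedom from bias, not a wrong inference.
- **The excluded group should be small.** The Efficacy-Evaluable set keeps clinical progression and pre-scan death. On its wording it also keeps patients whose only scans were not evaluable. Protocol 7.7 and 8.5.2 continue imaging after study drug stops, and Appendix 1 schedules CT or MRI at the end-of-treatment visit. This stands too, and zero is possible. Even the larger assumed shifts are well below the half-widths of about 16 to 19 points in the 25-treated examples.
- **A reader can rebuild the rate.** SAP 6.2.5 reports "Number of patients treated", and the responder count is normally the same in both sets. A possible exception is an expansion patient without measurable disease who has a complete response in non-target lesions. That allows a hand calculation, but the report would still lack the estimate and interval that it gives for DCR.
- **The stray rule may be carried-over text.** SAP 6.1 names SAF for OS and safety, so deleting the sentence from 6.3.1 would also remove the inconsistency. It would leave the primary efficacy endpoint without an all-treated rate, and 6.3.2 already uses SAF for an efficacy endpoint.
- **The protocol does not settle on confirmed response.** The ORR definition in Protocol 11.2.5 has no confirmation requirement, and Protocol 7.7 only says when a response counts as confirmed. Appendix 5 does call for confirmation in non-randomized studies with response as the primary endpoint. The label is therefore supported but minor.
- **Cohort 3 is a separate matter.** SAP Section 8 bases ORR, PFS and DOR on radiographic response or progression, which may explain the difference from Protocol 11.2.5, where PSA and lesions are combined. That bullet does not name the analysis set, although Section 8 does name it for OS.

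**Conclusion.** The concern holds. As written, the only ORR tables exclude some treated non-responders, the SAF rule in SAP 6.3.1 has no ORR table to act on, and the secondary DCR is handled more completely than the primary ORR. That reading is firm.

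The size is not known. With 25 treated and 7 or 8 responders, the overstatement is 2.4 to 2.8 points if two patients are unscanned, 5.3 to 6.1 points if four are, and none if all are scanned. These counts are assumptions. The figures cover missing scans only; they do not model Cohort 3 patients without measurable disease. The conflict between Protocol 11.2.1 and SAP 6.1 over those patients is real, and the documents do not show which version is intended. The plan should be changed, but nothing here invalidates the design.

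**What to change.** In SAP 6.3.1 and the linked sections:

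1. Add SAF tables of confirmed and nonconfirmed ORR, by dose level in escalation and by cohort in expansion. Count unassessed patients as non-responders, give exact 90% intervals as already planned for DCR, and place the tables beside the Efficacy-Evaluable ones. The Efficacy-Evaluable set may remain the prespecified set.
2. Label confirmed ORR as the primary version and nonconfirmed ORR as supportive.
3. Reconcile the Cohort 3 efficacy set between Protocol 11.2.1 and SAP 6.1. Record any intended change of set in SAP Section 8, next to the radiographic-response bullet.
4. Footnote the number of patients without measurable disease at baseline in the SAF tables and in the escalation Efficacy-Evaluable tables.

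The cost is a few tables, one label, one line in Section 8 and a footnote, with no new data. The all-treated ORR may be a few points lower than the prespecified one. SAF will also include some patients without measurable disease, which is why the footnote is needed.
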